## 4.3. Restrictions

Not applicable

## 4.4. Subject enrolment and randomization

Subject eligibility will be established before *enrolment*. Subjects will be *enrolled and randomized* strictly sequentially, as subjects are eligible *for randomization*. If a subject discontinues from the study, the subject number will not be reused, and the subject will not be allowed to re-enter the study.

Identified potential study subjects will be given thorough information regarding the study, both orally and in writing, by a physician. After the subject has been given the opportunity to ask any question regarding the study they will be asked to consent to study participation. If they do, they will sign the informed consent form.

At screening (before randomization): subjects will be assigned a unique subject identification (enrolment number).

At randomization, all eligible subjects will be given a randomization number that assigns them to one of the treatment groups. The randomization numbers are sequentially allocated to the subjects in the order of randomization. Each subject will receive only that treatment regimen which is labelled with the randomization number allocated to him/her.

If the subject fails to be randomized for any reason, the subject's identification and the reason for not being randomized will be entered into the eCRF. Note: The enrolment number is different from the randomization number.

Randomization will be performed with random assignment of treatment groups in the specified ratio of 1:1:1.

Subjects discontinuing treatment prematurely will not be replaced.

According to the recommendations given in the ICH E9 Guideline "Statistical Principles for Clinical Trials" (CPMP, 1998), the used block length is specified in a separate document, which is withheld from the study centre.

	Study code:	IPO-001	
Clinical Study Protocol	Version No:	5.1	
	Date:	26 MARCH 2019	

Subjects who fail to meet the eligibility criteria should not, under any circumstances, be enrolled or receive study medication. There can be no exceptions to this rule. Subjects who are enrolled, but subsequently found not to meet all the eligibility criteria must not be randomized or initiated on treatment, and must be withdrawn from the study.

Where a subject does not meet all the eligibility criteria but is randomized in error, or incorrectly started on treatment, the subject should be discontinued as soon as the error or incorrectness is evident, and returned to pre-study treatment, i.e. Duodopa.

### 4.5. Discontinuation and withdrawal of subjects

Subjects are free to discontinue their participation in the study at any time without prejudice to further treatment. The subjects may be withdrawn from the study at the discretion of the investigator due to safety concerns or if judged non-compliant with study procedures. In either case, serious adverse events will be followed up. Other reasons for discontinuing a subject are incorrect enrolment and subjects lost to follow-up.

#### 4.5.1. Premature termination of the study

The Investigator may terminate the study prematurely for any reasonable cause.

Furthermore, the Board of the Interim Study Analysis may terminate the study prematurely for any reasonable cause. It is also possible that the Board may suggest changes to the study design and procedures that will be implemented for the rest of the study. When such changes are implemented, they should be documented in an amendment to the study. If such an amendment is regarded as a major change, it should be approved by the Ethics Committee (EC) and Medicinal Products Agency (MPA).

Conditions that may warrant termination include, but are not limited to:

- The discovery of an unexpected, significant, or unacceptable risk to the subjects enrolled in the study.
- If MPA obtains information that raises doubts about the safety or scientific validity of the clinical study, MPA can suspend or prohibit the study.

If the trial is prematurely terminated or suspended, the investigator should promptly inform the subjects and ensure appropriate therapy and follow-up. Furthermore, EC and MPA will be informed promptly.

## 5. STUDY TREATMENTS

### 5.1. Identity of investigational medicinal products

Medical product (substance)	Dose, strength, route of administration	Manufacturer	Provided by
LCIG (Duodopa®) for treatment 3	Supplied in cassettes containing 100 mL of gel (20 mg/mL levodopa and 5 mg/mL carbidopa monohydrate) for intraintestinal administration	Fresenius Kabi Norge AS, Halden, Norway	Requisition from the pharmacy
Infudopa Active for treatment 1 and 2	Supplied in bottles containing 50 mL of solution (20 mg/mL levodopa and 2.5 mg/mL carbidopa) for i.v. or s.c. administration	Recipharm, Solna, Sweden	Manufacturer
Infudopa Buffer IntraV for treatment 1	Supplied in bottles containing 50 mL of solution	Recipharm, Solna, Sweden	Manufacturer
Infudopa Buffer SubC for treatment 2	Supplied in bottles containing 50 mL of solution	Unimedic, Matfors, Sweden	Manufacturer

#### Table 4. Product identity

#### 5.1.1. Doses and treatment regimens

All dosing during the study will be based on the patient's *regular day time hourly dose-requirement of Duodopa*. This consists of the regular continuous Duodopa dose (mg), plus the average accumulated daily extradoses (mg) divided by the regular daily infusion time (h). The morning Duodopa bolus dose is for the study set to 110% of the *regular day time hourly dose-requirement of Duodopa*. Consequently the *pre-study daily Duodopa dose* is for this study defined as:

The regular day time hourly dose-requirement  $\times$  (16 h – morning bolus infusion time h) + 110% of the regular day time hourly dose-requirement of Duodopa.

The total dose per day will be the sum of two components: morning bolus dose, and continuous (maintenance) dose given over a 16-h period. The combined i.v. infusion of Infudopa Active with Infudopa Buffer IntraV will be named Infudopa IntraV, and the combined s.c. infusion of Infudopa Active with Infudopa Buffer SubC will be named Infudopa SubC. In the following text doses and treatments apply to subjects in the second phase of the study (n=18). Before the start of this phase, it was decided that the bolus doses should be determined by a fixed percentage of the continuous hourly dose. The percentage chosen was for Infudopa IntraV 110%, for Infudopa SubC 155%, and for LCIG 110%. If clinically justified in the individual patient, the bolus dose may be adjusted, maintaining the relation 1 : 1.4 : 1 between the bolus doses for the different administration modes i.v : s.c : intestinal. The total dose is adjusted for the relative bioavailability based on AUC during the 0-16 h dosage interval vs. LCIG that was found in the interim study (ratio LCIG/Infudopa IntraV = 0.81; ratio LCIG/Infudopa SubC = 0.86).

Clinical Study Protocol		Study code:	IPO-001
	Clinical Study Protocol	Version No:	5.1
		Date:	26 MARCH 2019

Treatments will comprise the following therapy, where treatment 1 and 2 are considered investigational, and treatment 3 reference therapy:

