## Study design

IPO-001 is a prospective, randomized, 3-period cross-over, open-label multicentre trial comparing intravenous and subcutaneous Infudopa with intestinal Duodopa. The trial includes patients with Parkinson's disease who are on Duodopa treatment because of severe on-off manifestation when on oral levodopa. The patients will be identified and recruited at neurology clinics at university hospital clinical sites in Sweden, and travel from their living location to a clinical phase I site with full Good Clinical Practice (GCP) standard at the Sahlgrenska University Hospital in Gothenburg for the three treatment visits.

The subjects will be assessed at the phase I study clinic, where they during one treatment visit will receive Duodopa at optimal dosage for 16 hours, during another treatment visit will receive i.v. Infudopa at a rate estimated to yield corresponding serum levels of levodopa for the same duration, and at a third treatment visit will again receive the corresponding amount of levodopa but in the form of s.c. Infudopa. The study will hence have a cross-over design with a minimum of three days on Duodopa between the different treatment visits, where the order of treatments will be non-blinded but randomized.

Blood samples will be drawn according to a set schedule during the treatment visits, and subjects will be monitored for safety throughout the study, with focus on the local tolerability at the injection sites of i.v. and s.c. administration.

The duration of subject participation in the study is expected to be around 3-4 months from screening to final follow-up (with variation depending on subject's availability between treatment visits), and the subject will be on study treatment for in total 3 days (3x16 hours).

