#### Investigational product, dosage and mode of administration

Infudopa will be supplied in three different bottles: 1. Infudopa Active containing 20 mg/mL levodopa and 2.5 mg/mL carbidopa, 2. Infudopa Buffer IntraV, and 3. Infudopa Buffer SubC, the two latter with no active ingredients. Product 1 will be combined with product 2 for i.v. infusion, and product 1 with product 3 for s.c. infusion. After online mixing by two infusion pumps, Infudopa will contain 10 mg/mL levodopa and 1.25 mg/mL carbidopa. Each single dose treatment in the 3 dose groups below will be given during 16 h.

Dosing will be based on the patient's *regular day time hourly dose-requirement of Duodopa*. This consists of the regular continuous Duodopa dose (mg) plus the average accumulated daily extradoses (mg) divided by the regular daily infusion time (h). The morning Duodopa bolus dose is for the study set to 110% of the *regular day time hourly dose-requirement of Duodopa*. Consequently the *pre-study daily Duodopa dose* is for this study defined as:

The regular day time hourly dose-requirement  $\times$  (16 h – morning bolus infusion time h) + 110% of the regular day time hourly dose-requirement of Duodopa.

**Dose group 1.** Infudopa i.v. infusion will be given through an indwelling catheter placed in the arm. The total Infudopa i.v. dose will be 81% of the subject's individual *pre-study daily Duodopa dose*. Infudopa i.v. will be administered as a morning bolus dose followed by continuous i.v. infusion up to 16 h. The morning bolus dose will be 110% of the hourly continuous dose. The morning dose will not exceed 24 mL after mixing, corresponding to 240 mg levodopa. The expected 16-h levodopa dosage will be in total 492 to 2900 mg. The maximum daily dose levodopa during i.v. administration is not allowed to exceed 3240 mg (equal to 81% of the maximum allowed daily dosage for Duodopa that is 4000 mg).

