## 4.1. Inclusion criteria

For inclusion in the study, patients should fulfill the following criteria:

- 1. Signed informed consent
- 2. Male or female patients at least 30 years old
- 3. Patients with advanced Parkinson's disease who are already on LCIG (Duodopa®) for at least 30 days, on a stable treatment regimen of 600 mg to 4000 mg levodopa per day, and with approximately 16- or 24-h Duodopa infusion regimens
- 4. Patients with a Hoehn and Yahr (H&Y) score of ≤ 3 on Duodopa treatment (including concomitant medication)
- 5. Body mass index range from 18.0 to 35.0 kg/m^2
- 6. Patients in general good health, as judged by the Investigator, and as determined by vital signs, medical history, physical examination, ECG, and laboratory tests
- 7. Females of childbearing potential must have a negative pregnancy test prior to randomization and must be willing to use a highly effective contraceptive measure during relevant systemic exposure to the investigational drug and the first menstrual cycle after treatment cessation (see section 7.3).
- 8. Males must be willing to refrain from fathering a child, including sperm donation, during the study and 3 months following the last dose.

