#### 5.1.2. Dose adjustments during treatment and temporary interruptions of infusion

No extra LCIG infusion doses will be allowed (extra bolus doses are not possible to provide with the Infudopa pump system).

A movement disorder specialist will be present during the first 4 hours of treatment to clinically evaluate the efficacy of the given treatment and to adjust doses to avoid problematic under- or overtreatment. After the first 4 h the movement disorder specialist is available as needed for the

rest of the infusion period. If the subject experiences mild and easily endurable Off-symptoms or symptoms of overtreatment the infusion rate will not be changed. Non-levodopa containing medication such as benzodiazepines or paracetamol can be used as determined appropriate by the investigator. If a subject treated with Infudopa after the first hour of treatment is uncomfortably "OFF" by comparison to what he/she experiences with the regular treatment with Duodopa, the investigator can increase the infusion rate of Infudopa by 10-20%. Such increases may be repeated once in the following 2 h and on maximum two further occasions during the following treatment period. If the subject develops severe symptoms of overtreatment, such as uncomfortable dyskinesia, disturbing nausea, symptomatic hypotension or hallucinations, the infusion will be stopped for 10 minutes, reduced to minimum flow 1.4 mL/h for 20 minutes and then resumed at an infusion rate 20% lower than the preceding. The decision to stop infusion can be taken by the investigator or a study nurse who must immediately contact the investigator for further advice. A temporary stop of infusion may be repeated every second hour until symptoms are manageable or uncomfortable hypokinesia develops. All changes in infusion rates will be recorded.

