The subcutaneous maintenance infusion rate (maximum ca 17 mL/h mixed solution) is much lower than what is safely used for subcutaneous fluid hydration (60-70 mL/h). During the morning bolus a higher infusion rate (80 mL/h) will be used for up to 25 minutes (maximum 30 minutes). To avoid discomfort, the administration will be split to two subcutaneous infusion sites at each side of the abdomen. If despite this there is subject-reported subcutaneous oedema or pain in the infusion area, the infusion can be moved to another infusion site on the abdomen. If pain develops also at this site, the infusion must stop and the investigator must be contacted immediately. The infusion must also be stopped immediately if the subject develops signs of an allergic reaction in the infusion area (rapid development of itching or urticarial efflorescence) or in other parts of the body, in particular face and airways. Infusion must be stopped immediately at the occurrence of severe systemic events including but not restricted to: respiratory distress, chest pain, abdominal pain or impaired consciousness. The decision to interrupt infusion in the above cases can be made by a study nurse who will immediately contact a study physician and/or the investigator.

Oral levodopa–carbidopa or levodopa-benserazide will not be allowed until the last pharmacokinetic sample has been collected. If rescue medication is needed after the cessation of infusion, other non-levodopa and non-carbidopa medication will be used, for example benzodiazepines. If oral levodopa or carbidopa medication despite this is required prior to the last pharmacokinetic sample, a final blood sample will be taken prior to administration of oral drug.

Those subjects who receive infusion for more than 16 h/day prior to study start will have their pumps turned off after 16 h of infusion.

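### For eligible 24-h Duodopa users with a lower night rate, the dosing formula returns a 24-h mean instead of the daytime hourly requirement it names

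*Protocol*

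**What the plan says.** Section 5.1.1 opens the dosing rules with "All dosing during the study will be based on the patient's" day time hourly requirement, and defines it: "This consists of the regular continuous Duodopa dose (mg), plus the average accumulated daily extradoses (mg) divided by the regular daily infusion time (h". The synopsis gives the same definition under the heading on investigational product and dosage. The 16-h Duodopa dose is built from this figure. The i.v. and s.c. totals are then 81% and 86% of that dose, so all three visits inherit it.

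Inclusion criterion 3 (section 4.1) takes patients "on a stable treatment regimen of 600 mg to 4000 mg levodopa per day", "with approximately 16- or 24-h Duodopa infusion regimens". The only rule for the longer regimens is in section 5.1.2: "Those subjects who receive infusion for more than 16 h/day prior to study start will have their pumps turned off after 16 h of infusion". Nothing there or in 5.1.1 restricts the continuous dose, the extra doses or the divisor to daytime hours.

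The synopsis, under study design, describes the reference visit as one where patients "will receive Duodopa at optimal dosage for 16 hours". Section 5.1.2 has a movement disorder specialist present for the first 4 h "to adjust doses to avoid problematic under- or overtreatment".

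**The concern.** The name of the quantity and its formula disagree for one eligible subgroup. A patient infusing for 24 h has a regular daily infusion time of 24 h. Dividing by it averages the night hours into a figure that is then used to dose a 16-h day. If the night rate is lower, the maintenance rate at all three visits starts below the patient's own daytime rate, which does not fit the stated aim of optimal dosage.

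The available corrections are also uneven. The explicit rule allowing a 10 to 20% rate increase in section 5.1.2 is written for Infudopa only, and extra LCIG doses are barred. A patient started too low could therefore be stepped up more readily on the Infudopa visits than on the Duodopa visit. Such changes could enter the un-normalised AUC comparisons and the 2 to 16 h COV. The protocol gives nothing from which to size that effect.

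**Working it through.** **Reproducing the protocol's own dose figures.** With R the hourly requirement and the Duodopa bolus given at 40 mL/h × 20 mg/mL = 800 mg/h, the 16-h dose is D = R × (16 − 1.1R/800) + 1.1R.

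- Table 7 minimum maintenance of 28 mL over 16 h is 1.75 mL/h, so R = 35 mg/h and D = 35 × (16 − 0.048) + 38.5 = 597 mg, against 600 mg stated.
- The caps reproduce exactly: 0.81 × 4000 = 3240 mg and 0.86 × 4000 = 3440 mg.

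The formula is therefore being read as the protocol uses it.

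**Inputs for a 24-h user.** The protocol gives no night rates, no extra-dose amounts or timing, and no share of 24-h users. Assumed here: 16 day hours and 8 night hours, a day rate of 80 mg/h, a night rate of r × 80, and extra doses E (mg) all taken by day.

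- Formula as written: R = (80 × 16 + 80r × 8 + E)/24
- Daytime requirement: (80 × 16 + E)/16

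**Lower night rate, no extra doses (E = 0).** The ratio reduces to (16 + 8r)/24, whatever the day rate. The 16-h need is 80 × 16 = 1280 mg.

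| r | R as written (mg/h) | Against 80 mg/h | Study Duodopa dose D (mg) | Against 1280 mg |
|---|---|---|---|---|
| 1.0 | 80.00 | no error | 1359 | 6.2% above |
| 0.9 | 77.33 | 3.3% low | 1314 | 2.7% above |
| 0.8 | 74.67 | 6.7% low | 1269 | 0.8% below |
| 0.5 | 66.67 | 16.7% low | 1134 | 11.4% below |

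The 110% bolus adds about 6% to the total, so the total dose falls below need only when r is under about 0.82. The maintenance rate is low at any r below 1.

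**Infudopa visits.** The i.v. maintenance rate c solves c × (16 − 1.1c/600) + 1.1c = 0.81D. The s.c. rate solves c × (16 − 1.55c/800) + 1.55c = 0.86D. Each is 0.933 of its value under the daytime rate at r = 0.8, and 0.833 at r = 0.5, the same shares as for Duodopa.

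**Daytime extra doses, flat rate (r = 1).**

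- E = 100 mg: 2020/24 = 84.17 mg/h against 1380/16 = 86.25 mg/h, 2.4% low.
- E = 200 mg: 2120/24 = 88.33 mg/h against 1480/16 = 92.5 mg/h, 4.5% low.

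Both figures exceed the bare pump rate of 80 mg/h; they are low only against the requirement that includes extra doses. At an assumed day rate of 100 mg/h the same shortfalls are 2.0% and 3.7%.

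**Both together (r = 0.5, E = 200 mg).** 1800/24 = 75.0 mg/h, which is 18.9% below the 92.5 mg/h requirement and about 6% below the 80 mg/h pump rate.

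**Narrow reading of the sentence.** If the division applies to the extra doses only, the night rate drops out and the figure is 80 + E/24 against 80 + E/16, again 2.4% or 4.5% low. The continuous dose is given in mg, however, and becomes an hourly figure only if it too is divided.

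**The case against.** The label says day time wherever the quantity is used, and a sensible investigator may take both the continuous dose and the infusion time to be the daytime ones. That shows the intent, but the formula does not say so, and two investigators could dose the same 24-h user differently.

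The size rests wholly on assumed inputs. A 24-h user with a flat rate and no extra doses has no error, and the largest percentages come from the most extreme values chosen. This stands.

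The harm is limited. The specialist may adjust doses during the visit, Infudopa may be raised, and the bolus may be individually adjusted at a fixed ratio between routes. This also stands, subject to the unevenness between Infudopa and Duodopa visits.

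Four stronger readings are tempting, and the protocol does not support them:

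- That daytime extra doses alone set maintenance below the daytime pump rate. They do not: 84.17 and 88.33 mg/h are both above 80.
- That the total 16-h dose is always too small. At r = 0.9 with no extra doses it is 2.7% above need.
- That the comparison of routes is biased. Each patient's three doses scale from the same figure, so dose-normalised AUC ratios are not directly affected.
- That the dose tables prove the divisor wrong. A 24-h user at the 600 mg/day floor gets 600/24 = 25 mg/h (1.25 mL/h), below the Table 7 minimum of 1.8 mL/h. At a flat rate a daytime-only formula also gives 25 mg/h, so the mismatch does not isolate the divisor.

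**Conclusion.** The point holds for 24-h users with a reduced night rate. For them the written rule gives a 24-h mean, and the basis for all three visits is (16 + 8r)/24 of the daytime rate when there are no extra doses. The dilution of daytime extra doses is a separate and smaller matter, measured against the requirement that includes them.

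The existence of the error follows from the protocol text. Its size depends on the night/day ratio, the extra doses and the number of 24-h users enrolled, none of which the protocol states. For 16-h users the formula is correct. This is a dosing definition worth correcting for an eligible subgroup, and no effect on the trial's main bioavailability conclusion has been shown.

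**What to change.** In section 5.1.1 and in the synopsis, add that for patients who infuse longer than 16 h a day the requirement is the continuous dose plus extra doses given during the daytime period, divided by the hours of that period, with night-rate hours excluded. This also settles whether the division covers both terms.

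The cost is one sentence in two places. It needs no extra patients, visits or samples.

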#### Table 7. Dose Group 3, Duodopa

Levels in parenthesis should not be exceeded.

#### 5.1.2. Dose adjustments during treatment and temporary interruptions of infusion

No extra LCIG infusion doses will be allowed (extra bolus doses are not possible to provide with the Infudopa pump system).

A movement disorder specialist will be present during the first 4 hours of treatment to clinically evaluate the efficacy of the given treatment and to adjust doses to avoid problematic under- or overtreatment. After the first 4 h the movement disorder specialist is available as needed for the

rest of the infusion period. If the subject experiences mild and easily endurable Off-symptoms or symptoms of overtreatment the infusion rate will not be changed. Non-levodopa containing medication such as benzodiazepines or paracetamol can be used as determined appropriate by the investigator. If a subject treated with Infudopa after the first hour of treatment is uncomfortably "OFF" by comparison to what he/she experiences with the regular treatment with Duodopa, the investigator can increase the infusion rate of Infudopa by 10-20%. Such increases may be repeated once in the following 2 h and on maximum two further occasions during the following treatment period. If the subject develops severe symptoms of overtreatment, such as uncomfortable dyskinesia, disturbing nausea, symptomatic hypotension or hallucinations, the infusion will be stopped for 10 minutes, reduced to minimum flow 1.4 mL/h for 20 minutes and then resumed at an infusion rate 20% lower than the preceding. The decision to stop infusion can be taken by the investigator or a study nurse who must immediately contact the investigator for further advice. A temporary stop of infusion may be repeated every second hour until symptoms are manageable or uncomfortable hypokinesia develops. All changes in infusion rates will be recorded.

The subcutaneous maintenance infusion rate (maximum ca 17 mL/h mixed solution) is much lower than what is safely used for subcutaneous fluid hydration (60-70 mL/h). During the morning bolus a higher infusion rate (80 mL/h) will be used for up to 25 minutes (maximum 30 minutes). To avoid discomfort, the administration will be split to two subcutaneous infusion sites at each side of the abdomen. If despite this there is subject-reported subcutaneous oedema or pain in the infusion area, the infusion can be moved to another infusion site on the abdomen. If pain develops also at this site, the infusion must stop and the investigator must be contacted immediately. The infusion must also be stopped immediately if the subject develops signs of an allergic reaction in the infusion area (rapid development of itching or urticarial efflorescence) or in other parts of the body, in particular face and airways. Infusion must be stopped immediately at the occurrence of severe systemic events including but not restricted to: respiratory distress, chest pain, abdominal pain or impaired consciousness. The decision to interrupt infusion in the above cases can be made by a study nurse who will immediately contact a study physician and/or the investigator.

Oral levodopa–carbidopa or levodopa-benserazide will not be allowed until the last pharmacokinetic sample has been collected. If rescue medication is needed after the cessation of infusion, other non-levodopa and non-carbidopa medication will be used, for example benzodiazepines. If oral levodopa or carbidopa medication despite this is required prior to the last pharmacokinetic sample, a final blood sample will be taken prior to administration of oral drug.

Those subjects who receive infusion for more than 16 h/day prior to study start will have their pumps turned off after 16 h of infusion.

